4.5.2.5 Assessment of Relapses

Potential relapses should be recorded throughout the study period after screening. See Appendix 1 (Schedule of Assessments) for the timing of these assessments.

All new or worsening neurological events consistent with MS representing a "clinical relapse" are to be reported on the dedicated "MS relapse" form. A clinical relapse is defined as a monophasic clinical episode with patient-reported symptoms and objective findings typical of MS, reflecting a focal or multifocal inflammatory demyelinating event in the CNS, developing acutely or sub-acutely, with a duration of at least 24 h, with or without recovery, and in the absence of fever or infection (Thompson et al. 2018). Multiple sclerosis relapses should not be reported as an AE, unless they are serious.

It is recommended that women with new neurological symptoms suggestive of a relapse have an EDSS/Functional Systems Scores (FSS) assessment performed as soon as possible, ideally within 7 days of the onset of symptoms. However, it is not mandatory to perform an EDSS assessment in case of a suspected relapse.

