5.1.1.1 Adverse Events

According to the ICH, an adverse event is any untoward medical occurrence in a patient or clinical investigation patient administered a pharmaceutical product, regardless of causal attribution. An adverse event can therefore be any of the following:

- Any unfavorable and unintended sign (including an abnormal laboratory finding), • symptom, or disease temporally associated with the use of a medicinal product, whether or not considered related to the medicinal product.
- Any new disease or exacerbation of an existing disease (a worsening in the • character, frequency, or severity of a known condition), except as described in Appendix 5.
- Recurrence of an intermittent medical condition (e.g., headache) not present at • baseline.
- Any deterioration in a laboratory value or other clinical test (e.g., ECG, X-ray) that is • associated with symptoms or leads to a change in study treatment or concomitant treatment or discontinuation from study medicine.

Adverse events and serious adverse events related to MS are not considered for recording in the eCRF, unless they meet specific criteria. For more details, refer to Section 5.1.1.2.

5.1.1.2 Assessment of Serious Adverse Events and Non-Serious Adverse Events of Special Interest (Immediately Reportable to the Sponsor) and Other Non-Serious Adverse Events

Serious Adverse Events

A serious adverse event is any adverse event that meets any of the following criteria:

Is fatal (i.e., the adverse event actually causes or leads to death).

Ocrelizumab—F. Hoffmann-La Roche Ltd

- Is life-threatening. (NOTE: The term "life-threatening" refers to an event in which the patient was at immediate risk of death at the time of the event; it does not refer to an event that hypothetically might have caused death if it were more severe.)
- Requires or prolongs inpatient hospitalization.
- Results in persistent or significant disability/incapacity (i.e., the adverse event results in substantial disruption of the patient's ability to conduct normal life functions).
- Is a congenital anomaly/birth defect in a neonate/infant born to a mother exposed to study medicine.
- Is a significant medical event in the physician's judgment (e.g., may jeopardize the patient or may require medical/surgical intervention to prevent one of the outcomes listed above).

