The terms "severe" and "serious" are not synonymous. Severity refers to the intensity of an adverse event (e.g., rated as mild, moderate, or severe, or according to the National Cancer Institute Common Terminology Criteria for Adverse Events (NCI CTCAE) criteria; see Appendix 5); the event itself may be of relatively minor medical significance (such as severe headache without any further findings).

Severity and seriousness need to be independently assessed for each adverse event recorded on the eCRF (for detailed instructions, see Appendix 5).

Non-Serious Adverse Events of Special Interest

Adverse Events of Special Interest (AESI) for this study include the following:

- Cases of potential medicine-induced liver injury that include an elevated ALT or AST in combination with either an elevated bilirubin or clinical jaundice, as defined by Hy's law (see Appendix 5).
- Suspected transmission of an infectious agent by the study medicine, as defined below:

Any organism, virus, or infectious particle (e.g., prion protein transmitting transmissible spongiform encephalopathy), pathogenic or non-pathogenic, is considered an infectious agent. A transmission of an infectious agent may be suspected from clinical symptoms or laboratory findings that indicate an infection in a patient exposed to a medicinal product. This term only applies when a contamination of the study medicine is suspected.

A. Non-Serious Adverse Events other than Adverse Events of Special Interest

All non-serious adverse events (in addition to adverse events of special interest) must be collected for this study, and coded according to the appropriate level of Medical Dictionary for Regulatory Activities (MedDRA) classification.

B. Specific Adverse Events that are exempt from collection

Adverse events and serious adverse events related to MS are not considered for recording in the eCRF. Medical occurrences or symptoms of deterioration that are anticipated as part of MS or which are expected in the patient population studied should be recorded as an adverse event only if judged by the physician to have unexpectedly worsened in severity or frequency or changed in nature at any time during the study.

Following the above rationale, the following events will not be considered as adverse events for this study:

- 1. MS relapses.
- 2. Disability progression (increase in EDSS or other scales performed by the physician).

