5.1.2.2 Procedures for Recording Adverse Events

Investigator should use correct medical terminology/concepts when recording adverse events in the Adverse Event eCRF. Colloquialisms and abbreviations should be avoided.

Only one adverse event term should be recorded in the event field of the eCRF.

See Appendix 5 for further specific instructions regarding:

- IRRs
- Diagnosis versus signs and symptoms
- Adverse events occurring secondary to other adverse events
- Persistent or recurrent adverse events
- Abnormal laboratory values
- Abnormal vital sign values
- Abnormal liver function tests
- Deaths
 - All events with an outcome or consequence of death should be classified as serious adverse events and reported to the Sponsor immediately. In certain circumstances, however, suspected adverse reactions with fatal outcome may not be subject to expedited reporting (see Section 5.4). All deaths that occur during the protocol-specified adverse event reporting period, regardless of relationship to study medicine, must be recorded in the Adverse Event eCRF and immediately reported to the Sponsor.
- Worsening of pre-existing medical conditions
- Lack of therapeutic efficacy
- Hospitalization or prolonged hospitalization
- Overdoses, misuses, abuses, off-label use, occupational exposure, or medication error
- Quality defects, falsified medicinal products and product complaints
- Drug interactions

5.1.3 Reporting Requirements from HCP to Sponsor

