Death should be considered an outcome and not a distinct event. The event or condition that caused or contributed to the fatal outcome should be recorded as the single medical concept on the adverse event section of the eCRF. Generally, only one such event should be reported. The term **"sudden death"** should only be used for the occurrence of an abrupt and unexpected death due to presumed cardiac causes in a patient with or without pre-existing heart disease, within 1 hour after the onset of acute symptoms or, in the case of an unwitnessed death, within 24 hours after the patient was last seen alive and stable. If the cause of death is unknown and cannot be ascertained at the time of reporting, **"unexplained death"** should be recorded on the adverse event section of the

Ocrelizumab—F. Hoffmann-La Roche Ltd 127/Protocol MN42988, Version 3 CRF. If the cause of death later becomes available (e.g., after autopsy), "unexplained death" should be replaced by the established cause of death.

A5–3.9 PRE-EXISTING MEDICAL CONDITIONS

A pre-existing medical condition is one that is present at the baseline visit for this study. Such conditions should be recorded on the General Medical History and Baseline Conditions in the eCRF.

A pre-existing medical condition should be recorded as an adverse event only if the frequency, severity, or character of the condition worsens during the study. When recording such events in the adverse event section of the eCRF, it is important to convey the concept that the pre-existing condition has changed by including applicable descriptors (e.g., "more frequent headaches").

A5–3.10 LACK OF THERAPEUTIC EFFICACY

Events that are clearly consistent with the expected pattern of progression of the underlying disease should not be recorded as adverse events. These data will be captured as effectiveness assessment data only. In most cases, the expected pattern of progression will be based on EDSS score. In rare cases, the determination of clinical progression will be based on symptomatic deterioration. However, every effort should be made to document progression through use of objective criteria. If there is any uncertainty as to whether an event is due to disease progression, it should be reported as an AE. This exception from reporting includes events of disease progression with a fatal outcome which are clearly attributable to disease progression.

A5–3.11 HOSPITALIZATION OR PROLONGED HOSPITALIZATION

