Any adverse event that results in hospitalization or prolonged hospitalization should be documented and reported as a serious adverse event (per the definition of serious adverse event in Section 5.1.1), except as outlined below.

The following hospitalization scenarios are not considered to be serious adverse events:

- Hospitalization for giving birth
- Hospitalization that was necessary because of patient requirement for outpatient care outside of normal outpatient clinic operating hours
- Elective hospitalizations or surgical procedures that are a result of a patient's pre-existing condition(s) that have not worsened since receiving trial medication. Examples may include, but are not limited to, cholecystectomy for gallstones, and diagnostic testing. Such events should still be recorded as medical procedures in the concomitant procedures/treatments eCRF
- Hospitalization to receive trial medication such as infusions of ocrelizumab unless this is prolonged (more than 24 hours)

Ocrelizumab—F. Hoffmann-La Roche Ltd 128/Protocol MN42988, Version 3 • Hospitalization following an MS relapse as long as the reason for hospitalization is to receive standard treatment with IV methylprednisolone

A5–3.12 OVERDOSES, MISUSES, ABUSES, OFF-LABEL USE, OCCUPATIONAL EXPOSURE, OR MEDICATION ERROR

Any overdose, misuse, abuse, off-label use, occupational exposure, medication error (including intercepted or potential), or any other incorrect administration of medicine under observation should be noted in the Drug Administration section of the eCRF. Any overdose, abuse, misuse, inadvertent/erroneous administration, medication error (including intercepted or potential), or occupational exposure reports must be forwarded to the MAH with or without an AE.

Reports with or without an adverse event should be forwarded to the MAH as per nonserious timelines. If the associated adverse event fulfils the seriousness criteria, the event should be reported to the MAH immediately (i.e., no more than 24 hours after learning of the event, see Section 5.1.3.1).

For the purpose of reporting cases of suspected adverse reactions, an occupational exposure to a medicine means an exposure to a medicine as a result of one's professional or non-professional occupation.

A5–3.13 QUALITY DEFECTS, FALSIFIED PRODUCTS AND PRODUCT COMPLAINTS

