For each recorded adverse event (AE), the term entered by the investigator describing the event (the "reported term") will be assigned a standardized term (the "Preferred Term" [PT]) and assigned to a superclass term (the "System Organ Class" [SOC]) on the basis of the MedDRA WHO dictionary of terms version 26.1.

Definitions

Infant AE timepoints:

Neonatal (<28 days): AEs with an observed or imputed date of onset before the first 28 days of life.

Infant (≥28days): AEs with an observed or imputed date of onset on or after the 28 days of life.

Women AE timepoints:

Pregnancy: AEs with an observed or imputed date of onset before the infants' birth, i.e. during pregnancy. An AE with a completely missing, non-imputed start date will be assumed to be a pregnancy AE.

Pre-ocrelizumab postpartum: AEs with an observed or imputed date of onset on or after the infants' birth but before the start date of the first postpartum ocrelizumab infusion.

Post-ocrelizumab postpartum: AEs with an observed or imputed date of onset on or after the start date of the first postpartum ocrelizumab infusion.

Imputation of incomplete date: incomplete dates will be imputed as follows:

- If the start date is incomplete:
 - If the day is missing, impute to 01.
 - If the month is missing, impute to January.
 - If the date is completely missing, then the date will remain missing
- If the end date is incomplete:
 - If the day is missing, impute to the last day of the month
 - If the month is missing, impute to December
 - If the date is completely missing, then the date will be missing

Serious Adverse Events (SAEs): all SAEs including serious MS relapses and serious Infusion Related Reactions (IRRs).

Output Conventions

All analyses of AE data will be performed using the PTs unless otherwise specified.

For all summary tables, the AEs will be sorted by SOC (in decreasing order of overall incidence) and then by PT (in decreasing order of overall incidence). At each level of summarization (at least one event, SOC and PT), subjects reporting more than one AE will be counted only once. For AEs by grade (intensity), the highest grade will be reported.

The following summary tables will be generated for mothers and infants separately:

- Overview summary table of AEs, including: total number of subjects with at least one AE, total number of AEs, total number of deaths, total number withdrawn from study due to an AE, and total number of subjects with at least one:

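### Protocol 5.1.1.2(B) tells sites not to record MS-related SAEs, while Protocol 4.5.2.5 and SAP 4.8.2 treat serious MS relapses as reportable SAEs

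*Protocol*

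**What the plan says.** On relapses:

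- Protocol 4.5.2.5 (Assessment of Relapses): "Multiple sclerosis relapses should not be reported as an AE, unless they are serious". The same section sends every clinical relapse to a dedicated MS relapse form.
- Protocol 5.1.1.1 (Adverse Events): "Adverse events and serious adverse events related to MS are not considered for recording in the eCRF, unless they meet specific criteria". It refers to 5.1.1.2 for those criteria.
- Protocol 5.1.1.2, part B (events exempt from collection): "Adverse events and serious adverse events related to MS are not considered for recording in the eCRF", here without the proviso. Anticipated MS events are to be recorded "only if judged by the physician to have unexpectedly worsened in severity or frequency or changed in nature". A numbered list of events that are not adverse events follows, and MS relapses are item 1, with no condition attached.
- SAP 4.8.2 (Adverse Events) defines SAEs as "all SAEs including serious MS relapses and serious Infusion Related Reactions (IRRs".
- Protocol A5-3.11 lists one admission that is not an SAE: "Hospitalization following an MS relapse as long as the reason for hospitalization is to receive standard treatment with IV methylprednisolone".

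On deaths:

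- Protocol 5.1.2.2: "All deaths that occur during the protocol-specified adverse event reporting period, regardless of relationship to study medicine, must be recorded in the Adverse Event eCRF". A5-3.8 repeats this and classes fatal events as SAEs.
- Protocol A5-3.10, after exempting expected disease progression from AE recording: "This exception from reporting includes events of disease progression with a fatal outcome which are clearly attributable to disease progression".

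**The concern.** The SAP defines an output that depends on data which one protocol section tells sites to enter and another tells them to leave out. A woman with a relapse that meets a seriousness criterion is an SAE case under Protocol 4.5.2.5 and SAP 4.8.2. Under Protocol 5.1.1.2(B) she has no adverse event to enter unless the physician judges the relapse an unexpected worsening or a change in nature.

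Two things are at stake. One is the completeness of the maternal SAE counts and listing, which serve a stated safety objective (the rate and nature of adverse events in the mother). The other is timing: Protocol 5.1.3.1 requires SAEs to reach the sponsor within 24 hours whatever their relationship to the medicine, and a relapse that is never classed as an SAE does not trigger that rule.

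**Working it through.** The plan gives no figure to reproduce, so the check sets the rules side by side for specific cases.

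**Case 1: a relapse that meets a seriousness criterion but is not judged unexpected in severity, frequency or nature.**

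| Source | Entered as an SAE? |
|---|---|
| Protocol 4.5.2.5 | Yes, because it is serious |
| SAP 4.8.2 | Counted as an SAE |
| Protocol 5.1.1.2(B), opening sentence and list item 1 | No |
| Protocol 5.1.1.2(B), exception | Does not apply |

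Three texts might reconcile these rows:

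1. The proviso in 5.1.1.1. It points to 5.1.1.2, where the general criterion is unexpected worsening or change in nature. Seriousness is a separate concept, and 5.1.1.2 itself says that severe and serious are not synonyms. The list also shows that a seriousness condition could have been written: item 3, on MRI activity, has one and item 1 does not.
2. The statement in SAP section 4 that its analyses supersede those in the protocol. It governs analysis and cannot supply events that sites did not enter.
3. The MS relapse form. It preserves the relapse. But Protocol 5.1.2 asks for a seriousness assessment only for events recorded in the AE section of the eCRF, and the documents describe none for the relapse form. The SAP cannot be assumed able to rebuild serious relapses from it.

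None of the three resolves the case.

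**Case 2: a serious relapse judged unexpectedly worse or changed in nature.** It is recordable under 4.5.2.5 and, on a fair reading, under the exception in 5.1.1.2(B). The conflict is confined to Case 1.

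**Case 3: a relapse admitted only for standard IV methylprednisolone.** A5-3.11 says this admission is not an SAE. That narrows what counts as serious and fits with 4.5.2.5 and SAP 4.8.2. It is not a contradiction, although neither of those sections refers to it.

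**Case 4: a death clearly attributable to MS progression.** 5.1.2.2 and A5-3.8 require it in the AE eCRF; A5-3.10 exempts it. Both 5.1.2.2 and A5-3.8 allow that some fatal reactions may escape expedited reporting, but that is a different matter from eCRF recording. Their cross-references also differ: 5.1.2.2 points to 5.4, which contains no such exemption, and A5-3.8 points to A5-3.10.

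**Scale.** Protocol 1.3 cites a relapse in about 30% of women with MS in the first 3 months after delivery, and Protocol 6.1 plans about 33 women:

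- 0.30 × 33 = 9.9, so about 10 women with an early postpartum relapse on that rate.
- The share that would be serious is not in the documents. Purely as an assumption, 5% gives 9.9 × 0.05 = 0.5 events and 50% gives 9.9 × 0.50 = 5.0.
- One additional woman with an SAE moves the proportion by 1/33 = 3.0 percentage points.

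The tenfold width of that range shows that the number of affected events cannot be estimated. The cited rate is also a general MS figure, study women may resume ocrelizumab after birth, and the calculation does not remove Cases 2 and 3.

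**The case against.** The strongest reply is that little is lost in practice. Every clinical relapse goes on its own form, and SAP 4.6.4 summarises relapses by 3-month interval and lists them. Sites receive training and an eCRF manual (Protocol 7.2), and discrepant data are queried (7.1). Neither the manual nor the eCRF is available here, so the relapse form may already carry a seriousness field. The exempt list is introduced as following from the unexpected-worsening rationale, so it need not mean that a relapse can never be an AE. The study's primary endpoint is infant B-cell levels, and no tests are planned.

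Much of this stands. A reader might infer that relapses drop out of the dataset; they do not. What is exposed is the SAE classification and the prompt reporting that follows from it. A reader might also infer that the SAE and death tables as a whole cannot be filled consistently, or that sites will certainly diverge. The documents show neither: most SAE rows are unaffected, and training could produce uniform practice. But training material cannot be taken to cure a contradiction in the protocol, and uniform practice under 5.1.1.2(B) would still leave out events that SAP 4.8.2 says it counts.

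On deaths, a reader might infer that maternal deaths in general could go unrecorded. Only deaths clearly attributable to MS progression are in conflict; every other death is recorded under all the sections. SAP 4.8.2 also counts total deaths separately from AEs with a fatal outcome, although it names no separate source for that count.

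**Conclusion.** The rules on serious MS relapses contradict each other: Protocol 4.5.2.5 and SAP 4.8.2 on one side, Protocol 5.1.1.2(B) on the other. The proviso in 5.1.1.1 does not close the gap, because the criterion it leads to is not seriousness. This is an internal inconsistency, wrong as written, and should be corrected. The conflict over eCRF recording of deaths due to MS progression is real but minor, and the documents give no rate for such deaths.

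The number of events affected is small and not estimable from the documents. It is tempting to turn the cited 30% relapse rate into a count of missing SAEs, but the serious share has no source, so no such count is claimed. The conclusion rests on the text alone and on one condition: that some site follows 5.1.1.2(B) as worded for a serious relapse that is not judged unexpected. The consequence is limited to descriptive maternal safety outputs and 24-hour reporting; the primary endpoint is not touched.

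**What to change.** 1. Reconcile Protocol 4.5.2.5, 5.1.1.1 and 5.1.1.2(B) into one recording rule for serious relapses, with a cross-reference to A5-3.11 for what counts as serious. Which rule to adopt is for the sponsor.
2. Align the SAE definition in SAP 4.8.2 with that rule. If serious relapses stay off the AE page, add a seriousness field to the MS relapse form (if it has none) and have the SAP take serious relapses from there.
3. Reconcile 5.1.2.2 and A5-3.8 with A5-3.10 on eCRF recording of deaths due to MS progression, and make the cross-references agree.

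The cost is a protocol clarification and a wording change in the SAP, possibly one extra eCRF field and a few more SAE entries. Sample size, visits and the primary analysis do not change.

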5.1.2.1 Adverse Event Reporting Period

Investigator will seek information on adverse events at each patient contact. All adverse events subject to the collecting and reporting requirements outlined in this protocol, whether reported by the patient or noted by study personnel, will be recorded in the patient's medical record and in the Adverse Event eCRF.

Adverse events will be reported throughout the study and until the last study visit for both mother and infant. After this period, the investigator should report any serious adverse events that are believed to be related to prior study drug treatment. Adverse events that

occur in a pregnant woman pre- and post- study should be reported to the marketing authorization holder (MAH), as a follow up spontaneous pregnancy report to the initially spontaneously reported pregnancy, by following the standard pharmacovigilance reporting process for post-marketing pregnancy cases.

